1.4 How will the results of this trial be used?

The study will yield effect sizes for primary endpoints of sexual desire and sexual distress that we will use in a subsequent larger RCT application. This study will advance health-related knowledge by providing new data on the relative efficacy of online CBT and MBT for FSD and health outcomes by having the potential to increase access to effective treatment for women living in rural and remote areas as well as those who experience other barriers in accessing face-to-face care. Thus, this research program has a high likelihood of filling a major gap in healthcare of women and eSense has significant potential for commercialization. UBC's University-Industry Liaison Office has committed to supporting this project through to commercialization (see Letter of Support, **Appendix**).

I ([name]) have expertise with Knowledge Translation (KT) methods. I have held KT grants from CIHR (DGE129657) and MSFHR (#17403, 2017-18; #18793, 2019-20) for social media campaigns, and received UBC's 2020 President's Award for Public Education through Media for KT output. As Executive Director, Women's Health Research Institute, I supervise skilled research managers who have advanced training in KT and implementation science. For this project, we will use integrated and end-of-grant KT, and have an established patient advisory group with whom we meet twice/year. We plan to publish the pilot RCT findings (given dearth of relevant publications). The findings will also be disseminated through traditional conference and rounds presentations, an infographic video, and a public forum for women, co-designed with our patient advisory group. The forum information will be used to design our future RCT.

1.5 Are there any risks to the safety of participants involved in the trial?

Owing to the sensitive nature of sexual content in the intervention, participants will have the option to contact the coordinator (supervised by licensed psychologists [name] and [name]) for guidance on sexually-based concerns. After data have been cleaned and checked (Q2 Y3), participants will be provided unrestricted access to content in both intervention arms, which they can use at their leisure. This adds no cost to our budget. Privacy will be maintained and absolutely no identifying information will be linked to data.

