Assessment points: CONSORT²⁸ guidelines will be followed in terms of tracking number of participants recruited, randomized, and retained through assessment and treatment. For CBT-O and MBT-O groups, there are 3 assessment points (baseline; post-treatment (within 2wks of completing the 8-module program); and 6-month follow-up). For the wait-list group, there are 2 pre-treatment assessments at waiting period start and after randomization to treatment (4 assessment points; same online questionnaires). No treatment will be given to wait-list participants during this waiting period. However, after the second online questionnaires are complete, they will be randomized to either the CBT-O or MBT-O arm of eSense. All participants will also be sent a mid-treatment link to an online question that asks them to write freely about their reactions to the treatment to date. This is included to examine quality assurance of the intervention. To minimize attrition, honoraria will be linked to completion of each assessment point: \$30 for (each) baseline assessment, and \$40 at post-treatment and 6-month follow-up assessment points.

Protocol: All participation will be remote, requiring no in-person meetings. Prospective participants will contact the study coordinator at UBC via e-mail, then set up a phone screen for inclusion/exclusion criteria (Fig 1). Consent forms will be sent to prospective participants prior to the scheduled phone screen by the study coordinator. Women will be informed of the length of the intervention (8 modules; 8-12 wks), expectations for homework (1-2 hours/week), and the use of treatment navigators. After meeting the screening criteria, the study coordinator will send prospective participants a personalized link to a Qualtrics questionnaire battery. The first page of the questionnaires will be the e-consent form. Participants must read and electronically sign the consent form before they move on to the baseline questionnaires. The e-consent form will indicate that any questions/issues they raise in interactions with study staff that are worrisome (e.g., suicidal ideation) will automatically prompt the coordinator to contact them. Women who choose not to participate will be provided with other resources (websites, directories of sex therapists, books).

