2.8-2.9 What are the proposed 1° and 2° outcome measures? How are they measured at follow up?

Our primary outcomes are clinical— sexual desire and sexual distress—and will be used to determine effect sizes needed for a future large RCT. Secondary outcomes will be used to refine the interventions. Questionnaires take ~30min and are completed at all assessment points using Qualtrics.

1° outcomes: Sexual distress will be measured by the Female Sexual Distress Scale-Revised⁹⁰ (FSDS-R), used extensively in women’s sexuality treatment outcome studies. Sexual desire will be measured by the The Sexual Interest and Desire Inventory (SIDI).

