2° outcomes: Treatment satisfaction will be assessed with (i) two face-valid single item measures measured on through the eSense platform at the beginning of modules 2-8 and measures via Qualtrics a week after completing module 8 asking participants to rate helpfulness of content covered in the previous module, and ease of reading the content (1-10 scale); Research suggests a cut-off of 6.5/10 on these measures to indicate acceptable utility and clarity of content⁹⁴; (ii) qualitative feedback about website and homework assignments collected by treatment navigators; (iii) adapted Erectile Dysfunction Inventory of Treatment Satisfaction,⁹⁵ a widely used scale measuring satisfaction after treatment for erectile dysfunction. Perceived relationship with navigators is assessed at post-treatment with two measures: (i) Empathy subscale of the Barrett-Lennard Relationship Inventory,⁹⁶ a valid measure of perceived provider empathy that predicts outcomes in CBT⁹⁷; (ii) perceived navigator effectiveness with the Working Alliance Inventory, Short Form.⁹⁸ Treatment compliance will be measured by: (i) recording number of weeks and treatment sections completed⁹⁹; (ii) eSense website engagement and performance by Google analytics (e.g., page views, # visits/sessions, page views/visit, visit duration, unique/returning users); these metrics are recommended by the E-CONSORT guidelines as important for e-health intervention studies. The platform used to house eSense tracks views of a page and completion of the overall program, enhancing and complementing what analytics can provide; (iii) navigators will ask participants to rate homework completion on a Likert scale ranging from “did not attempt” to “successfully completed all assignments” weekly; (iv) having participants complete the Homework Rating Scale-II (HRS-II)¹⁰⁰ at the beginning of modules 2-8 on the eSense platform and then complete it again week via Qualtrics after completing module 8 to provide a comprehensive measure of experience with the homework; (v) measuring navigator adherence to study guidelines by coding a random 20% of Zoom sessions (participants will be informed of these recordings) for adherence (to be done by [name]’s trainee; no funding requested), using a previous adherence scale we have used.^{17,81} Sexual function will be measured using the total score of the Female Sexual Function Index,⁹¹ a validated self-report measure of sexual function.

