2.10 What is the proposed sample size; justification for assumptions underlying power calculations?

Based on our findings,¹⁷ we expect large effect sizes for the main outcomes ($d=.8$ for FSFI and $d=1.05$ for FSDS-R) in the MBT-O arm. According to power analysis based on these two measures and two treatment

groups, 75 participants are needed to give us 90% power to discover a large size effect of our treatment at alpha level of .05 (PASS, 2019 Power Analysis and Sample Size Software (2019). NCSS, LLC. Kaysville, Utah, USA, [ncss.com/software/pass.](http://ncss.com/software/pass/)). Based on [name]'s work, we expect ~30% attrition so we will recruit 129 women (n=43 per arm) (control later randomized to treatment). After attrition, we expect to have n=30 in each arm.

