Compliance: We will compare compliance rates to previous research. One systematic review¹⁰⁴ found a typical adherence rate of ~50% in internet interventions for anxiety and depression. Given the aspects of our study meant to maximize adherence (e.g., engaging web content, individualized support, reminder e-mails), we expect our rates to be at least this high. Rates of treatment completion will be compared to other trials of online treatments for FSD and to web-based interventions more broadly. Systematic reviews of drop-out rates from online therapy with minimal support suggest typical attrition of ~30%.¹⁰⁵ Reported rates in online treatment of FSD are comparable (35%)⁷³ or higher (54%).⁸³ We will compare our attrition rate to 30% using a one-sided binomial test, to determine if it is significantly higher in our study.

Alternate Treatment: We will propose to participants who report no significant improvement after a year try the alternate treatment. We will also ask participants who drop out if they are willing to try the alternate treatment (if time is not a factor). We will not be collecting data in the alternate treatment as this is not a true test of their participation given that they will have already received one treatment.

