2.15 How many centres will be involved?

Though the team of investigators come from 4 different institutions, all study activities will take place in the NPA's laboratory at UBC.

2.16–2.18 What is the proposed type of analyses? What is the proposed frequency of analyses?

Statistical analysis: Effect of treatment will be determined by analyzing baseline (pre) to post-treatment changes after CBT-O and MBT-O on sexual distress (FSDS-R) and sexual desire (SIDI) scores. Sustainability of treatment effects will be evaluated by adding the follow-up measurement point to the model. Both analyses will be conducted using a multilevel mixed effect model analysis with one within-subject factor of time (treatment) based on 2 or 3 measurement points (baseline and post-treatment in the first analysis; plus 6-month follow-up for the second analysis) and one between-subject factor (CBT-O vs MBT-O) as well as their interaction. Interactions will test for differences in the amount of change due to treatment between arms. We will calculate effect sizes and confidence intervals (CI) and use descriptive statistics for measures of treatment satisfaction and compliance. These values will be compared between treatment arms. Treatment length will vary from 8 to 12 wks, so individual length of treatment will be added as a control variable in all initial models. Notable differences will guide changes that may increase satisfaction/compliance before we conduct a larger RCT following completion of the current pilot study.

Missing data: Mixed-effects modelling allows for missing data and uses all available data for estimating model parameters. Incomplete outcome data can restrict the sample size available for tests of interactions. We will impute missing outcome data using multiple imputation techniques. We will run a sensitivity analysis to compare analysis that uses multiply-imputed data to analysis that includes missing data.

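### No stated due date for the primary outcomes of women who stop early, and a missing-data check whose agreement would not show robustness

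*Combined protocol and SAP*

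**What the plan says.** - **Timing (section 2.6-2.7).** The CBT-O and MBT-O groups have three assessments: baseline, "post-treatment (within 2wks of completing the 8-module program", and 6 months. The date from which the 6 months run is not given. The assessments are assigned to the groups as a whole, and payment is tied to assessments, not to modules. The mid-treatment contact is a free-text question without FSDS-R or SIDI.
- **Attrition (section 2.10).** The plan recruits 129 women, 43 per arm, allowing for about 30% loss: "After attrition, we expect to have n=30 in each arm".
- **Adherence and retention (section 2.13-2.14).** A cited review "found a typical adherence rate of ~50% in internet interventions for anxiety and depression". Attrition is given as a separate quantity: about 30% in general, and 35% and 54% in online treatment of FSD. E-mail reminders, two further e-mails and a telephone call cover missed sessions and scheduled measures.
- **Analysis (section 2.16-2.18).** A mixed model on available data is followed by multiple imputation (MI), and then: "We will run a sensitivity analysis to compare analysis that uses multiply-imputed data to analysis that includes missing data". The imputation model is not described, and no not-at-random analysis is stated. In addition, "individual length of treatment will be added as a control variable in all initial models".
- **Compliance data (section 2.8-2.9).** These include "recording number of weeks and treatment sections completed".
- **Purpose.** Section 1.4: "The study will yield effect sizes for primary endpoints of sexual desire and sexual distress". Section 2.8-2.9 says that the primary outcomes "will be used to determine effect sizes needed for a future large RCT".

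**The concern.** Completing module 8 is the only stated trigger for the post-treatment battery. The reminder system chases measures that are scheduled, but nothing in the supplied text schedules this one for a woman who leaves at, say, module 4. Adherence and attrition are treated as different things, so some women may stop the program and still be reachable. Their outcomes could be collected if a date existed, and cannot be recovered later if they are not.

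The planned check does not make up for this. A mixed model on available data, and MI from the same variables, rest on the same missing-at-random assumption. Comparing them mostly shows Monte Carlo noise. A reader who sees close agreement could take it as reassurance that it does not give.

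The pilot's main product is at stake: the pre-post effect sizes carried into the design of the larger trial.

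**Working it through.** **1. The plan's own figure.** 30/(1 - 0.30) = 42.9, so 43 per arm; 3 x 43 = 129; 43 x 0.7 = 30.1. This reproduces section 2.10. The expected loss is 129 - 90 = 39 women. The section does not say at which assessment the 30% applies.

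**2. Size of a possible bias.** Let m be the share without an outcome, C the mean change in observed women, and k the missing women's change as a fraction of C. Then bias = m x C x (1 - k).

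Inputs from section 2.19 (face-to-face MBT): FSDS-R 32.3 - 22.9 = 9.4; SIDI 27.9 - 16.9 = 11.0. The d values there are per SD of change, since 6.43/sqrt(58) = 0.84 (0.85 stated) and 8.13/sqrt(59) = 1.06. The documents do not give k, so a range is shown. With m = 0.30:

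| k (assumed) | FSDS-R points | SIDI points | FSDS-R, SD of change |
|---|---|---|---|
| 1.5 | -1.41 | -1.65 | -0.13 |
| 1 | 0 | 0 | 0 |
| 0.5 | 0.30 x 9.4 x 0.5 = 1.41 | 0.30 x 11.0 x 0.5 = 1.65 | 0.30 x 0.425 = 0.13 |
| 0 | 0.30 x 9.4 = 2.82 | 0.30 x 11.0 = 3.30 | 0.30 x 0.85 = 0.26 |

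Positive values overstate the change. The last column holds the SD constant. If the SD widens with the mixture, by sqrt(1 + 0.3 x 0.7 x D^2) where D is the difference in change in SD units, the column becomes -0.11, 0, 0.14 and 0.30.

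FSDS-R at other values of m, for k = 0.5 and k = 0: 15% gives 0.70 and 1.41; 35% gives 1.65 and 3.29; 54% gives 2.54 and 5.08.

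**3. Can the planned comparison show this?** Simulation for distress: n = 129, 30% missing, 1,500 runs, 30 imputations, no auxiliary variables, assumed baseline-to-post correlation 0.5. Results are in SD of change:

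| k | True change | Mixed model | MI | Mean absolute gap |
|---|---|---|---|---|
| 1.5 | 0.980 | 0.850 | 0.850 | 0.007 |
| 1 | 0.851 | 0.848 | 0.849 | 0.007 |
| 0.5 | 0.724 | 0.854 | 0.854 | 0.008 |
| 0 | 0.596 | 0.854 | 0.853 | 0.007 |

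The truth moves by almost 0.4 SD. Both estimates stay at 0.85, and the gap between them does not change. For k = 1, 0.5 and 0, the gap is 0.007-0.008 at correlations 0.3 and 0.7, and 0.011 with n = 65.

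**4. Auxiliary variables.** With one assumed homework auxiliary (correlation 0.3, 1 SD lower in early stoppers), MI moves to 0.77-0.78 in all four cases. The two methods then differ, but MI still does not follow the truth.

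**5. Measuring early stoppers.** If half of them are measured and completion status is in the imputation model, MI gives 0.978, 0.850, 0.722 and 0.596, close to the truth. This holds because, in the simulation, the measured stoppers represent the unmeasured ones.

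**6. Comparison of the two programs.** Assume 20% missing in one arm, 40% in the other, and k = 0. The true arm difference is 9.4 x (0.8 - 0.6) = 1.9 FSDS-R points. In a simulation with 64 women per arm, both methods showed about 0.1. With 30% missing in both arms and the same k, no material difference arises.

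**The case against.** **Retention is provided for.** Section 2.6-2.7 gives the assessments to whole groups, and section 2.13-2.14 provides reminders and calls. This stands. A reader might infer that early stoppers will not be assessed, and the documents do not say so: nothing withholds the battery from them. What remains is that no date is stated on which it falls due.

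**Dates may sit in Fig 1 or the Appendix timeline.** This also stands. The point is limited to the supplied text, and if those pages carry a date, the timing part falls.

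**No analysis of observed data can show how unmeasured women changed.** Correct, and it applies equally to delta-adjusted MI, which displays dependence on an assumption and detects nothing. It does not rescue the planned comparison, which shows neither.

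**The imputation model is not described and may use auxiliaries.** True, so the near-agreement is a property of the standard form and not of every possible implementation. Section 2.16-2.18 also never claims that agreement excludes bias. It is nevertheless the only sensitivity analysis for missing outcomes.

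**Sampling error is of similar size.** At d = 0.85 the standard error is about sqrt(1/90 + 0.85^2/180) = 0.12 with 90 women, and about 0.17 with 45 in one active arm. A half-benefit bias of 0.13 SD is therefore about one standard error or less. That is fair on proportion, but a confidence interval reports sampling error and does not report this bias.

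**Treatment length.** A reader might infer that the length-of-treatment covariate would exclude early stoppers, or that 1-2 weeks per module (8 x 1 to 8 x 2 = 8-16 weeks) contradicts the 8-12 weeks in sections 2.2 and 2.16-2.18. The documents support neither. Weeks completed are recorded, and 8-12 weeks is given in section 2.2 as an average and an estimate. These are missing details only.

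**Conclusion.** The point holds as a gap that should be closed, not as a demonstrated bias. On the supplied text, early stoppers have no stated due date for FSDS-R and SIDI, and the 6-month point has no stated start. The one planned sensitivity analysis, in standard form without auxiliaries, would look the same whether unmeasured women did better, equally or worse.

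At 30% missing, the illustrative error in mean FSDS-R change runs from an understatement of 1.4 points to an overstatement of 2.8; for SIDI, from 1.7 to 3.3. These figures are not bounds. They rest on face-to-face changes carried over to an online program, on 30% lacking an outcome, and on assumed values of k.

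Two stronger conclusions are tempting. One is that the effect sizes will be overstated. The direction is unknown: women may leave because the program is not helping, or because they have improved. The other is that the CBT-O versus MBT-O comparison is biased. That requires drop-out, or change among drop-outs, to differ by arm, and the documents give no evidence of either.

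**What to change.** 1. **Assessment date.** Keep completion as the trigger for completers. State a latest date, counted from treatment start and late enough to allow the permitted time per module, at which every woman not yet assessed is sent the post-treatment battery whatever module she reached. Anchor her 6-month battery to that date.
2. **Sensitivity analysis.** Describe the imputation model and include completion status and sections completed in it. Add a delta-adjusted MI analysis over a stated range in both directions, including no change from baseline, with the shift allowed to differ by arm. Present it as showing how far the effect sizes depend on the assumption, not as a test of whether unmeasured women differed.

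**Cost.** Protocol and analysis wording, some extra analysis, and online batteries of about 30 minutes. Honoraria come to at most about 39 women x 2 batteries x $40 = $3,120 at 30% attrition. Section 2.6-2.7 already provides the $40 per battery, so this may not be new spending; the budget was not supplied. The downside is that a few slow participants may be assessed before they finish.

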Both arms will be supplemented by treatment navigators (*who provide no formal therapy*) (e.g., exploring and challenging negative beliefs about sexual activity). Their role will be clearly described to participants as helping them engage with and navigate through the content. Navigators will meet weekly via Zoom with participants while they are completing the intervention. Each of these weekly sessions will take place on a UBC Zoom account held by the navigator, and each session will be video recorded. Once recorded, it will be labelled by participant ID and module number, and deleted from the Zoom server. Then it will be moved to our lab’s OneDrive account. With structured training and ongoing supervision led by the PI ([name]) and Drs. [name] and [name], navigators provide (a) encouragement to engage in the treatment; (b) accountability for completing homework assignments; and (c) answers to practical questions (e.g., “what if I keep falling asleep while meditating?”).⁸⁴ [name] (CoA) has expertise in training navigators. In her online intervention study (n=260) she developed a navigator training manual and peer support method which will be used.

Participants will have flexibility in the amount of time (1-2 weeks) they spend on each module, as other studies^{73,85} have shown flexibility helps with efficacy and real-world utility.⁸⁶ Our timeline estimates 8-12 weeks to complete all 8 modules. We will record time required for participants to complete 8 modules.

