2.11 If applicable, are health service research issues to be addressed?

This pilot is aimed at establishing effect sizes, so we will include health economics in a future larger RCT.

2.12 What is the planned recruitment rate? How will the recruitment be organized? Over what time period will recruitment take place? What evidence is there that the planned rate is achievable?

We will use the combination of methods we often use to recruit women with sexual difficulties.^{9,17,43} These include: (i) online postings (e.g., social media, Craigslist, women-specific groups); (ii) sending letters to ~100 BC primary care providers to request they inform patients about the study; (iii) paid advertisements in newspapers; and (iv) posted recruitment ads in the community on public boards (e.g., gyms, community centres, coffee shops, etc.). We have made a commitment to oversampling for trans women, given evidence that they face high levels of sexual dysfunction and tend to be omitted in research.¹⁰¹ We tailor our methods to ensure a consistent rate of recruitment, and will check sampling every 3 months to ensure we are accessing potential populations of trans women. We are not including trans men or non-binary individuals because the online materials refer to "women" throughout.

2.13–2.14 Are there likely to be any problems with compliance? On what evidence is this based? What is the likely rate of loss to follow up? On what evidence is this based?

Adhering to navigator schedule: If participants exhibit a consistent difficulty in scheduling Zoom sessions and/or has difficulty accessing a webcam of high enough quality to allow for effective interaction, we will allow participant-navigator meetings to take place by phone.

Attrition: Strategies to minimize attrition include: engaging intervention materials; trained, dedicated navigators; explicit discussion of required time commitment; and stepped compensation schedule. The study coordinator will send participants and navigators reminder e-mails about all Zoom sessions (on the day before) and reminders to complete online measures. Two more e-mails will be sent if there is no response.¹⁰² If participants still do not engage in a session or complete scheduled measures, they will be phoned by the study coordinator.¹⁰³

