2.19 Has any pilot study been carried out using this design?

As detailed in section 1.2, we have spent 2 years developing the CBT-O program of eSense and completing 3 feasibility and usability studies. The MBT-O arm content has been developed, tested, and found effective in a face-to-face format. In 2014, we received CIHR funding (MOP-136876) for a 5-year RCT of 8 sessions of group MBT vs sex education/sex therapy for women (cis, trans) with low desire.⁸⁷ The trial included 12-month follow-up and was completed in Dec 2019. 70 women (mean age 39y, range 20y-66y) completed the MBT arm, providing measures of sexual distress (FSDS-R) and sexual desire (sexual interest/desire inventory). Average relationship length was 11y, 81% were Euro-Caucasian, and 75% identified with sexual attraction towards men. Following MBT, we found significant improvement in female sexual distress [paired t-test, $t(57)=6.43$, $p<.001$, Cohen's $d=0.85$ (mean at time 1: 32.3; mean at time 2: 22.9)] and sexual desire [$t(58)=-8.13$, $p<.001$, Cohen's $d=1.06$ (mean at time 1: 16.9; mean at time 2: 27.9)]. We are now writing the manuscript of primary outcomes.⁸¹

In parallel, supported by another 5-year CIHR grant (MOP-123271), we applied MBT to 130 women with Provoked Vestibulodynia (a chronic genital pain condition) and compared it to CBT. We found 8-week MBT was superior to 8-week CBT for improving self-reported pain with vaginal penetration.⁴⁶ Improvements in pain, sexual function, and psychological domains persisted at least 1 year. On all other endpoints, MBT and CBT groups were highly effective and had clinically significant outcomes.

Our findings confirm our ability to create distinct CBT and MBT interventions for sexual dysfunction that are feasible and highly efficacious (all pre- to post-effect sizes were $d>0.90$), with benefits lasting up to 12 months follow-up. Since all of these interventions have been delivered in a face-to-face format, the next step to increase access is to move the programs online.

3 – TRIAL MANAGEMENT**3.1 What are the arrangements for day-to-day management of the trial?**

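### The visible text gives no post-treatment assessment date for women who stop early, and the only missing-data sensitivity analysis need not reveal overstated improvement if they respond less well

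*Combined protocol and SAP*

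**What the plan says.** - **Timing (2.6-2.7, Assessment points).** The two program groups have three assessments: baseline, post-treatment and 6 months. Post-treatment is defined as "post-treatment (within 2wks of completing the 8-module program". No starting point is given for the 6 months. Honoraria are tied to assessments, not to modules.
- **Outcomes (2.8-2.9).** FSDS-R and SIDI are collected only at these assessments. The mid-treatment contact is a single free-text question.
- **Chasing (2.13-2.14, Attrition).** After e-mail reminders, "If participants still do not engage in a session or complete scheduled measures, they will be phoned by the study coordinator".
- **Treatment length.** Section 2.2 states "We will record time required for participants to complete 8 modules". Section 2.16-2.18 says "individual length of treatment will be added as a control variable in all initial models". Section 2.8-2.9 lists "recording number of weeks and treatment sections completed" among the compliance measures.
- **Missing data (2.16-2.18).** A mixed model uses all available data, and missing outcomes are multiply imputed. The only check is: "We will run a sensitivity analysis to compare analysis that uses multiply-imputed data to analysis that includes missing data".
- **Purpose (1.4).** "The study will yield effect sizes for primary endpoints of sexual desire and sexual distress", for use in planning a larger trial.
- **Expected loss.** Section 2.10 plans for about 30% attrition. Section 2.13-2.14 cites 35% and 54% in earlier online treatment of female sexual dysfunction.

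**The concern.** The only visible trigger for the post-treatment battery is finishing all eight modules. A woman who stops at module 3 never reaches it. If 6 months runs from post-treatment, her follow-up has no date either. Her answers might be obtainable, but nothing says when to ask for them.

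This matters because the effect of treatment is defined as change from baseline to post-treatment in FSDS-R and SIDI, and those effect sizes are the pilot's main product. If early stoppers improve less than finishers and their scores are absent, the pre-post effect is too large. The planned check would not necessarily show it. Standard multiple imputation and a likelihood-based mixed model both fill the gap, explicitly or implicitly, from women who did answer and had similar observed data. Agreement between them says little about whether the unobserved women did worse.

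The documents give no reasons for stopping, so poorer response among stoppers is an inference.

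**Working it through.** **1. The plan's own attrition figure.** 30 / (1 - 0.30) = 42.9, rounded up to 43 per arm; 43 x 3 = 129. This reproduces section 2.10. The check below therefore uses 30% as the plan's own expectation and 54% as the highest rate it cites.

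**2. Size of improvement (section 2.19, face-to-face mindfulness trial).**
- FSDS-R: "mean at time 1: 32.3; mean at time 2: 22.9", so change = 32.3 - 22.9 = 9.4. d = 6.43/sqrt(58) = 0.84 (stated 0.85). SD of change = 9.4/0.844 = 11.1.
- SIDI: change = 27.9 - 16.9 = 11.0. d = 8.13/sqrt(59) = 1.06 (stated 1.06). SD of change = 11.0/1.058 = 10.4.

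**3. Overstatement when stoppers are unobserved.** Assume finishers improve by the amounts in step 2 and stoppers by a fraction f of that. With share q missing, overstatement = q x (1 - f) x change.

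| q | f | FSDS-R | SIDI |
|---|---|---|---|
| 30% | 0.5 | 0.30 x 4.7 = 1.41 | 0.30 x 5.5 = 1.65 |
| 30% | 0 | 0.30 x 9.4 = 2.82 | 0.30 x 11.0 = 3.30 |
| 54% | 0.5 | 0.54 x 4.7 = 2.54 | 0.54 x 5.5 = 2.97 |
| 54% | 0 | 0.54 x 9.4 = 5.08 | 0.54 x 11.0 = 5.94 |

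In standardised terms for FSDS-R at q = 30%, the mean is divided by the SD of change with the mixture variance added:
- f = 0.5: 7.99 / sqrt(11.13² + 0.21 x 4.7²) = 0.70.
- f = 0: 6.58 / sqrt(11.13² + 0.21 x 9.4²) = 0.55.

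Both compare with 0.84 in finishers.

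**4. Would the planned check show it?** Simulation: 64 women per program (about 129/2 once wait-list women are re-randomised), 600 replicates, 20 imputations, baseline SD 10 assumed, 30% missing. FSDS-R improvement in the first arm:

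| f | True, all women | Mixed model | Multiple imputation | Mean absolute gap between the two |
|---|---|---|---|---|
| 1 | 9.32 | 9.34 | 9.35 | 0.13 |
| 0.5 | 8.03 | 9.52 | 9.53 | 0.13 |
| 0 | 6.58 | 9.41 | 9.42 | 0.14 |

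The two methods agree equally well whether or not there is bias. In a second simulation (n = 129, 1,000 runs, SD 11.1, baseline-post correlation 0.5 assumed, imputation from baseline only), f = 0 gave true 6.51, available-data 9.33 and imputed 9.33. A delta adjustment of the correct size gave 6.52.

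**5. How much could a dated battery recover?** If a fraction r of stoppers answers, at 30% stopping, the remaining FSDS-R overstatement is (0.70 x 9.4 + 0.30 x r x f x 9.4)/(0.70 + 0.30r) minus the true mean (6.58 for f = 0; 7.99 for f = 0.5).

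| r | f = 0.5 | f = 0 |
|---|---|---|
| 0 | 1.41 | 2.82 |
| 0.25 | 0.96 | 1.91 |
| 0.50 | 0.58 | 1.16 |
| 0.75 | 0.27 | 0.53 |

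The documents do not give r. This assumes that those who answer represent those who do not.

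**6. Between programs.** With equal loss and equal f the bias cancels: at 30% in both arms and f = 0, the true difference was 0.07 and the mixed-model estimate 0.05. With 20% against 40% loss and f = 0, the true difference was 1.84 points and both methods estimated about zero (-0.05 and -0.07).

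**7. Allowed pace.** Section 2.2 allows 1-2 weeks per module, so 8 x 1 = 8 to 8 x 2 = 16 weeks. The 8-12 weeks stated there is an estimate, not a limit.

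**The case against.** The case on the other side has real force.

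- **The schedule may sit elsewhere.** Fig 1 and the timeline appendix are not visible, so a calendar date there cannot be ruled out. This stands, and the point is limited to the visible text.
- **The plan looks as if it means to assess everyone.** Assessments are assigned to the groups rather than to finishers, payment follows assessments, and retention in assessment and in treatment are both tracked. The two-week window may simply be the normal timing. A reader might infer that non-completers are excluded from assessment; nothing says so. What is missing is when they would be assessed.
- **Early stoppers are chased.** A reader might infer that the telephone call bypasses them because they have no scheduled measure. It does not: a missed session also triggers it, and sessions are weekly. The call still sets no date for the battery.
- **Treatment length need not be undefined.** A reader might infer that the covariate removes early stoppers from the model. That follows only if length means time to finish all eight modules. The weeks recorded as a compliance measure could supply a value, though the plan does not say they will.
- **The imputation model is unspecified.** Both simulated methods used little beyond baseline, so their agreement is close to built in. Homework, helpfulness and engagement data could move the imputed result somewhat. They would not remove dependence on an unobserved response, so the claim is only that the check need not reveal the bias.
- **Switching programs.** A reader might infer that outcomes will be contaminated when drop-outs try the other program. Section 2.13-2.14 sets no earliest time for that offer, so an early switch is permitted but not planned. It is a minor point.

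**Conclusion.** The concern holds for the visible text. No rule says when an early stopper is assessed, and the sole missing-data comparison rests, in standard form, on missing-at-random on both sides. With about 30% attrition expected, within-program change could be overstated without the check showing it.

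The illustrative size is 1.4 to 2.8 FSDS-R points and 1.7 to 3.3 SIDI points. It assumes that finishers improve as in the face-to-face mindfulness trial, that stoppers improve half as much or not at all, and that all 30% lack outcomes. It also applies the 30% to all 129 women, although some loss may occur during the wait-list period.

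Two stronger readings should be resisted. These figures are not the effect of the missing date: they describe attrition bias in general, and the part a dated battery would remove depends on how many stoppers would answer. Nor is bias in the CBT-O versus MBT-O comparison shown: that needs loss or shortfall to differ by arm, and the documents give no evidence that it will.

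The change is worth making because it is cheap and because outcomes not collected on time cannot be recovered.

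**What to change.** 1. **Sections 2.6-2.7.** Send the post-treatment and 6-month batteries to every woman randomised to a program, at entry or after the wait list, regardless of modules completed. For those who have stopped, use a fixed time from program start consistent with the allowed pace: for example 12-14 weeks, or 16-18 weeks (8 modules x 2 weeks, plus the 2-week window). Count 6 months from that date.
2. **Sections 2.16-2.18.** Add a delta-adjusted missing-not-at-random sensitivity analysis by arm, for example reducing imputed improvement by 0 to 9.4 FSDS-R points and 0 to 11 SIDI points (about 0 to 1 SD of change). Include early-stop status in the imputation model. Use the weeks recorded as a compliance measure as treatment length for early stoppers.
3. **Sections 2.13-2.14 (minor).** Offer drop-outs the other program only after their post-treatment and 6-month batteries are due, and analyse by randomised arm.

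**Cost.** Extra honoraria are at most 0.30 x 129 = 38.7, about 39 women, x 2 x $40 = $3,120; at 54%, about 70 women x 2 x $40 = $5,600. There is a little more analysis, and drop-outs wait longer for the other program. Batteries and reminders already exist, and the sample size does not change.
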